2.2. Endpoints**2.2.1. Efficacy Endpoints****2.2.1.1. Primary Efficacy Endpoints**

- Compare the treatment group difference in the mean improvement from Baseline to Day 85 in CLASI Activity scores of those in the efficacy analysis set receiving RSLV-132 and those receiving placebo.
- Compare the treatment group difference in the mean improvement from Baseline to Day 169 in CLASI Activity scores of those in the efficacy analysis set receiving RSLV-132 and those receiving placebo.

2.2.1.2. Secondary Efficacy Endpoints

Compare the treatment group difference on the following endpoints:

- Improvements (from baseline to Day 85 and Day 169) in the SLEDAI-2K, BILAG-2004, and PGA scores
- Improvement (from Baseline to Day 85 and Day 169) in the FACIT-Fatigue scale
- Improvements (from Baseline to Day 85 and Day 169) in tender or swollen joint count
- Reduction in oral steroids at day 169 relative to Day 85

- The proportion of subjects achieving a 50% improvement in CLASI Activity score

2.2.1.3. Exploratory Efficacy Measures

- Evaluate the differences on the gene expression profiles between the two treatment groups
- Evaluate the difference on the autoantibody and complement profiles between the two treatment groups
- Evaluate the difference on the serum protein levels between the two treatment groups
- Compare the mean improvement (from Baseline to Day 85; or Baseline to Day 169) in CLASI damage scores of those randomized to be treated with RSLV-132 and those randomized to receive placebo.

2.2.2. Safety Measures

- Reported adverse events
- Changes in laboratory values and vital signs from baseline
- Evaluate the immunogenicity of RSLV-132 as measured by the presence of RSLV-132 antibodies

2.3. Study Design

2.3.1. Study Population

This is a Phase 2a, multi-center, double-blind, placebo-controlled study to evaluate the impact of 13 intravenous infusions of RSLV-132 in subjects with Systemic Lupus Erythematosus. The study population will be 18 to 70 years male or female with SLE, including cutaneous manifestations of SLE and a CLASI score of ≥ 10 at Screening, and elevated levels of any one of the Ro-52/60, La, Sm, SmRNP, U1 RNP A/68 autoantibodies at Screening (local or central laboratory).

Approximately 50 subjects will be enrolled at approximately 15-20 clinical centers in the United States. Study subjects who are eligible for enrollment and have provided written informed consent will be randomized 2:1 (Active:Placebo) to receive 13 infusions of 10 milligram per kilogram (mg/kg) of RSLV-132 or Placebo.

2.3.2. Treatment Groups and Dosing

Following Baseline evaluations on Day 1, randomized subjects will receive their first infusion of RSLV-132 or Placebo. RSLV-132 or Placebo will be administered intravenously at 10 mg/kg at baseline, then weekly for two weeks and then once every 2 weeks for the next 20 weeks (13 administrations) to subjects with SLE.

RSLV-132 shall be prepared for each subject from individual stock vials provided by Sponsor. Details of dilution, dose preparation, and administration instructions will be provided in the Study Drug Reference Manual. The dose for each individual shall be based on the subject's baseline body weight.

2.3.3. Study Visits and Assessments

Potential subjects will be screened to assess their eligibility to enter the study within 28 days prior to study entry (i.e., prior to Baseline visit). Following Baseline evaluations on Day 1, randomized subjects will receive their first intravenous infusion of RSLV-132 or Placebo. Subjects will return to the research unit for additional visits as described in Table 1 Study Procedures.

Subject participation duration: 28 days of screening followed by 22 weeks of treatment and 8 weeks of follow up (approximately 34 weeks total). The duration of the study from Baseline visit to End of Study visit, excluding the screening period is approximately 30 weeks for each subject. Study assessments are outlined in Table 1.

Table 1: Study Procedures

Study Procedures	Screen (-28 to -1)	Baseline Day 1	Day 8	Day 15	Day 29	Day 43	Day 57	Day 71	Day 85	Day 99	Day 113	Day 127	Day 141	Day 155	Day 169 (EOT)	Day 215 (EOS)
Acceptable Visit Window (days)			+3	+3	+3	+3	+3	+3	+3	+3	+3	+3	+3	+3	+5	+5
Informed Consent	X															
Inclusion/exclusion	X	X ^a														
Demographics	X															
Weight, height	X															
Hepatitis, HIV tests	X															
Physical exam	X	X ^b			X ^b	X ^b										
Pregnancy tests	X ^c	X ^d														X ^c
AE assessment		X	X	X	X	X	X	X	X	X	X	X	X	X	X	X
Medical/medication history	X	X ^e														
Vital signs	X	X	X	X	X	X	X	X	X	X	X	X	X	X	X	X
Chem-20, CBC, UA	X	X			X		X		X		X		X		X	X

Study Procedures	Screen (-28 to -1)	Baseline Day 1	Day 8	Day 15	Day 29	Day 43	Day 57	Day 71	Day 85	Day 99	Day 113	Day 127	Day 141	Day 155	Day 169 (EOT)	Day 215 (EOS)	
Acceptable Visit Window (days)			+3	+3	+3	+3	+3	+3	+3	+3	+3	+3	+3	+3	+3	+5	+5
SLEDAI, BILAG, PGA, joint count		X			X		X		X		X		X		X		
CLASI	X	X			X		X		X	X	X	X	X	X	X	X	
Photographs of cutaneous disease	X	X							X							X	
FACIT index		X							X							X	
Serum for study drug concentration		X			X				X							X	X
Serum for protein analysis		X							X							X	
Serum for RNase activity		X			X				X							X	X
Whole blood for gene expression		X			X				X							X	X
Serum for autoantibody, C3, C4 profile	X	X			X		X		X		X		X		X		

Study Procedures	Screen (-28 to -1)	Baseline Day 1	Day 8	Day 15	Day 29	Day 43	Day 57	Day 71	Day 85	Day 99	Day 113	Day 127	Day 141	Day 155	Day 169 (EOT)	Day 215 (EOS)	
Acceptable Visit Window (days)			+3	+3	+3	+3	+3	+3	+3	+3	+3	+3	+3	+3	+3	+5	+5
Serum for ADA		X		X	X				X								X
Study Drug administration		X ^f	X	X ^f													

^a CLASI activity and damage score and confirm no changes in SLE medications only

^b directed physical exam

^c serum pregnancy test for women of childbearing potential (6.5)

^d urine pregnancy test for women of childbearing potential (6.5)

^e interim medical/medication history only

^f RSLV-132 or placebo shall be administered according to the infusion rate and time set forth in the Study Drug Reference Manual

2.3.4. Concomitant Medications

Subjects entering the study who had no changes to their SLE medications in the previous 30 days prior to the Baseline visit shall remain on the background medications at the same doses throughout the study. With the exception of decreases in Oral Corticosteroids (OCS), no changes in lupus medications shall be permitted during the study, including the addition of topical steroids or topical tacrolimus, except for the rescue of a lupus flare.

2.3.4.1. Steroid Tapering

One of the objectives of the study is to evaluate the potential steroid sparing effects of RSLV-132. Steroid doses should remain stable through Day 85. Therefore, Investigators shall decrease the use of oral corticosteroids beginning on Day 85 using the guidance below. No further steroid decreases should occur from Day 141 through Day 169.

- Subjects receiving >7.5 milligram (mg) of prednisone or equivalent daily AND demonstrating a clinical improvement in the cutaneous manifestations of lupus as measured by a decrease in the CLASI activity by 50% compared with Baseline shall decrease oral corticosteroids as follows:
 - Decrease prednisone (or equivalent) by 2.5 mg/day
 - If the prednisone dose (or equivalent) remains greater than 7.5 mg/day AND cutaneous disease activity remains improved (CLASI activity score decreased by 50% compared with baseline) AND prednisone has been stable for 2 weeks, reduce prednisone by an additional 2.5 mg; repeat after 2 more weeks.
 - If prednisone reduced to 7.5 mg, see below,
 - If after a decrease in prednisone, the CLASI is no longer decreased (compared to baseline) by 50%, the investigator may increase the prednisone to the previous daily dose (not to exceed the baseline dose)
- Subjects receiving ≤ 7.5 mg/of prednisone or equivalent daily AND demonstrating clinical improvement in the cutaneous manifestations of lupus as measured by a decrease in the CLASI activity score by 50% compared with baseline, the investigator may, at his/her discretion, decrease prednisone by no greater than 2.5 mg/day every other week.

2.3.4.2. Treatment of Flares

Investigators should treat lupus flares as they deem appropriate with the minimum amount of corticosteroid necessary and should return the subject to baseline steroid dose as quickly as medically reasonable. Should a subject require more than steroids for a lupus flare, investigators should treat as necessary and notify the medical monitor.

2.3.5. Subject Withdrawal

Subjects will be informed that they are free to withdraw from the study at any time and for any reason. The Investigator may remove a subject from investigational treatment if, in the Investigator's opinion, it is not in the best interest of the subject to continue. Notification of discontinuation of investigational treatment will be made immediately to the Sponsor. In case of premature discontinuation of investigational treatment, efforts will be made to perform all End of Treatment (EOT) assessments and an End of Study (EOS) visit outlined in SAP Section 2.3.3 Table 1.

If a subject wishes to withdraw from the study, the site staff should confirm whether the subject is agreeable to continue the assessments without the investigational treatment or if they wish no further involvement in the study. In the latter case no further study-related evaluations will be performed and no additional data will be collected.

The date and the reason for discontinuation of investigational treatment or withdrawal from the study will be recorded on the subject's Case Report Form (CRF). Subjects that withdraw after receiving study drug will not be replaced.

2.3.6. Randomization and Blinding

This will be a double-blind, placebo-controlled study. As such, except for the specifically designated unblinded study site pharmacist, the investigator, sponsor, and remaining study site clinical staff will be blinded as to treatment. Ongoing drug accountability will be monitored by an unblinded monitor.

A randomization code will be computer-generated by a contract research organization (CRO) Axio Research LLC. Subjects meeting the study entry criteria will be randomized via an interactive web response system (IWRS). Subjects will be randomized in a 2:1 ratio to either RSLV-132 or Placebo. The randomization schedule will be generated by the randomization statistician at Axio Research (who is not on the project team) or designee and maintained in a secure and limited-access location separate from the study investigator and members of the project team. The study subject, investigative staff, the Sponsor, the Sponsor study team (includes contractors and vendors), excluding the unblinded study site pharmacist and unblinded monitor mentioned above, will be blinded to treatment assignments during the study.

Except in a medical emergency, the investigator or designee and blinded study site clinical staff will remain blinded during the conduct of the study and until database lock.

If any other unblinding event occurs in addition to the ones mentioned above, it will be documented in a separate document other than this SAP.

2.3.7. Sample Size and Power

The sample size of approximately 50 subjects chosen for this study was based upon precedent set by other studies of similar nature and was not based on power calculations. Therefore no formal hypothesis testing will be performed.

P-values obtained from the analyses, if they are generated, will be used for obtaining information only and will be evaluated at the two-sided alpha level of 0.05.

3. GENERAL CONSIDERATION FOR DATA ANALYSES

3.1. Analysis Sets

3.1.1. Intent-to-Treat Analysis Set

The Intent-to-Treat (ITT) Analysis Set is defined as all subjects who were randomized, regardless of whether the subject actually received any study drug (RSLV-132 or Placebo). The subject will be included in the treatment group to which they were randomized.

3.1.2. Full Analysis Set

The Full Analysis Set (FAS) is a modified ITT and is defined as all subjects randomized who received at least one dose of study drug (RSLV-132 or Placebo). The subject will be included in the treatment group to which they were randomized. The Full Analysis Set is equivalent to the Efficacy Analysis Set defined in the study protocol and can be used interchangeably. For the purpose of generating the summary tables and by subject listings under the description of this SAP, the term of Full Analysis Set will be used.

3.1.3. Safety Analysis Set

The Safety Analysis Set (SAS) is defined as all subjects who received any treatment with either RSLV-132 or placebo.

Randomized subjects that receive the incorrect therapy from that intended will be summarized in the group according to the therapy actually received. Subjects who are not randomized but who receive treatment or placebo will also be included and summarized according to the therapy actually received. In the unlikely event of a subject commencing one study therapy and crossing over to the other, the data for that subject will be included in summaries and analyses with the original group.

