### 11.5 Subject Population for Safety Analysis

The safety of RSLV-132 will be compared between the two arms using the following safety parameters: adverse events, previous and concomitant medications, previous and concomitant diseases and laboratory data. The safety population will include all patients who received any treatment with either RSLV-132 or placebo. Randomized patients that receive the incorrect therapy from that intended will be summarized in the group according to the therapy actually received. Patients who are not randomized but who receive treatment or placebo will also be included in the safety population and summarized according to the therapy actually received. In

the unlikely event of a patient commencing one study therapy and crossing over to the other, the data for that patient will be included in summaries and analyses with the original group.

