10.1. Adverse Events

Adverse events will be coded using the Medical Dictionary for Regulatory Activities (MedDRA version 19.0 or higher) adverse event dictionary. If a subject experiences multiple events that map to a single preferred term, the greatest severity (by grade) and strongest investigator assessment of relationship to study drug will be reported for the applicable summaries.

Treatment-emergent adverse events (TEAE) are defined as events for which the date of onset is on or after the date of first dose of study drug (RSLV-132 or Placebo). Where an adverse event

(AE) collected after the date of first dose with a partially or fully missing start date or time, and it is unclear as to whether the AE is treatment emergent, it will be assumed that it is treatment emergent.

The number and percentage of subjects with adverse events will be summarized by treatment group. The percentages will be calculated based on the number of subjects in each treatment group of the SAS. System organ class (SOC) and preferred term (PT) within each SOC will be presented in descending frequency of RSLV-132 group. Subjects will be counted only once for each SOC and PT.

All adverse events (treatment-emergent and non-treatment-emergent) will be listed.

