10.1.2. Incidence of Adverse Events

Subjects with at least one treatment-emergent adverse event will be summarized by SOC, PT, and by treatment group. The incidence rate (IR) of the event per 100 patient years for each SOC and PT as well as the overall patient years of each treatment group will be calculated. IR of the event per 100 patient years will be calculated as $(\text{Total \# of Events} / \text{Patient Year}) * 100$. Patient year will be calculated as the $(\text{Total study drug exposure} / 365.25)$. Total study drug exposure will be defined as the sum of $[(\text{Last visit date} - \text{First dose date}) + 1]$.

Treatment-emergent adverse event summary by PT with descending order of frequency in the RSLV-132 group will also be presented by treatment group.

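### The crossover sentence in the safety-set rules would report a placebo starter's post-switch RSLV-132 data under placebo, and it leaves a single later wrong infusion unassigned

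*SAP*

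**What the plan says.** The Safety Analysis Set in SAP 3.1.3 is "defined as all subjects who received any treatment with either RSLV-132 or placebo". The section then gives grouping rules. The general one is: "Randomized subjects that receive the incorrect therapy from that intended will be summarized in the group according to the therapy actually received". Treated subjects who were never randomized are also grouped by what they received. The last sentence covers mixed therapy, which the plan regards as unlikely. When a subject begins on one therapy and then switches, "the data for that subject will be included in summaries and analyses with the original group". Protocol 11.5 carries the same rule: "the data for that patient will be included in summaries and analyses with the original group". Neither document says whether the original group is the randomized arm or the first therapy received.

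The later safety sections inherit this grouping:

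- **AE percentages (SAP 10.1).** "The percentages will be calculated based on the number of subjects in each treatment group of the SAS". An event is treatment-emergent if it starts on or after the first dose of either therapy. Each subject is counted once per system organ class and preferred term.
- **Incidence rates (SAP 10.1.2).** "Total study drug exposure will be defined as the sum of" the days from first dose to last visit, inclusive. Time is not divided by therapy.
- **Immunogenicity (SAP 10.3).** Positive and negative ADA results are summarized by treatment group on the safety set, among subjects with a sample at each visit.

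Efficacy is separate: SAP 3.1.2 groups the Full Analysis Set as randomized.

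**The concern.** Safety tables should set events beside the exposure that may have caused them. The first grouping rules in SAP 3.1.3 do this, but the crossover sentence does not. A subject who starts on placebo and later receives RSLV-132 contributes every later AE, ADA result and day of follow-up to placebo. That takes an event away from the active group and adds it to the comparator, which is the unfavourable direction for a safety comparison.

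The problem is one-sided. An RSLV-132 starter who later receives placebo stays under RSLV-132, which is reasonable given the half-life of about 16 days in protocol 3.4.1.

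ADA is the clearest example. Immunogenicity is a secondary objective (protocol 4.2), and protocol 3.4.1 and 3.4.2 report no positive or confirmed positive subjects in the two earlier studies. A single positive caused by RSLV-132 but tabulated under placebo could be taken for assay background.

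The wording also leaves two cases open. A single wrong infusion partway through fits both the incorrect-therapy sentence and the crossing-over sentence. And a subject randomized to RSLV-132, given placebo by mistake at the first infusion and then treated correctly 12 times, belongs to RSLV-132 or to placebo depending on how the original group is read.

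**Working it through.** The plan gives no figure on this point, and its sample size has no power basis (protocol 11.6, SAP 2.3.7), so there is nothing to reproduce. The check is a reading of the text followed by simple arithmetic.

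**1. Reading.** Take a placebo-randomized subject who receives one RSLV-132 infusion at a later visit. The incorrect-therapy sentence points to RSLV-132; the crossing-over sentence points to placebo. SAP 10.1, 10.1.2 and 10.3 have no rule by therapy at onset that would separate the data afterwards.

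**2. Group sizes.** About 50 subjects at 2:1 (SAP 2.3.1): 50/3 ≈ 17 placebo and 33 RSLV-132.

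**3. Infusions at which the harmful case could arise.** The subject must start on placebo, which leaves 12 of the 13 infusions: 17 × 12 = 204. The trial total is 50 × 13 = 650, so this is 204/650 = 31%. Both counts assume full dosing, and neither is a probability.

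**4. Effect on a percentage.** One placebo starter crosses and then has an event in a category with no earlier event:

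- current rule: placebo gains 1/17 = 5.9 percentage points;
- subject counted under RSLV-132: 1/(33 + 1) = 1/34 = 2.9%.

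If the subject already had an event in that category, the placebo numerator does not change. For ADA, the 1/17 figure applies at a visit only if all 17 placebo subjects have a sample.

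**5. Effect on the rate per 100 patient-years.** Assume every subject is followed from Day 1 to Day 215, so 215 days each.

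- Current rule: placebo patient-years = 17 × 215/365.25 = 10.01. One event gives 100/10.01 ≈ 10.0 per 100 patient-years.
- For a switch on day s, pre-switch days = s − 1 and post-switch days = 215 − (s − 1). If RSLV-132 time starts at the first RSLV-132 infusion, RSLV-132 patient-years = (33 × 215 + post-switch days)/365.25.

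| Switch day | Pre-switch days | Post-switch days now counted as placebo | Share of 215 | RSLV-132 patient-years, time split | One event per 100 patient-years |
|---|---|---|---|---|---|
| 8 | 7 | 208 | 97% | 19.99 | 5.0 |
| 85 | 84 | 131 | 61% | 19.78 | 5.1 |
| 155 | 154 | 61 | 28% | 19.59 | 5.1 |

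**6. Why the time must be split.** Moving the whole subject to RSLV-132 would give 34 × 215/365.25 = 20.01 patient-years. For a Day 155 switch, 154 of that subject's 215 days (72%) would be placebo-period time in the RSLV-132 denominator, which slightly lowers the active rate. Regrouping alone is therefore not enough.

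**The case against.** The strongest reply is that this is a deliberate, prespecified rule for a rare contingency. A reader might infer that the two sentences flatly contradict each other. The documents do not support that: the crossover sentence can be read as a specific exception for mixed therapy beside a general rule for subjects given the wrong therapy. That part of the reply stands. What it leaves is a departure from the as-received principle, an undefined original group, and no precedence for a single later wrong infusion.

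The controls also count. Assignment is by interactive web response system (SAP 2.3.6), an unblinded pharmacist prepares placebo and keeps the drug records (protocol 8.2 and 8.5), and an unblinded monitor checks compliance and accountability (protocol 13.1). No crossover is planned.

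Three stronger readings on size are tempting and should be set aside:

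- A reader might take all 650 infusions as opportunities for harm. Only later infusions in placebo starters matter, and without an error rate even 204 says nothing about likelihood.
- A reader might infer that every misplaced subject moves a placebo rate by 5.9 points. Because subjects are counted once per term, this needs a post-switch event in a category with no earlier one.
- A reader might infer that a drug signal would be hidden. All AEs are listed (SAP 10.1), deviations are listed and major ones summarized (SAP 6.3), and serum drug concentration is scheduled at Days 29, 85, 169 and 215 (protocol Appendix A). A case could be traced, and p-values are descriptive only (SAP 5).

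Traceability does not correct the tables, though. With no data monitoring committee (SAP 4), the final summaries are the main between-group safety comparison the plan provides.

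**Conclusion.** The point holds in a narrow form and is minor. When triggered by a placebo starter who receives RSLV-132, the stated rule places post-switch AEs, ADA results and patient-time in the wrong column, and no later section undoes this. One such subject with a new event category adds 5.9 percentage points to placebo, against 2.9% if counted under RSLV-132. On the rate scale, one event is about 10.0 per 100 patient-years under placebo, against 5.0 to 5.1 under RSLV-132 with time split at the switch.

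These figures assume a 33:17 split and follow-up to Day 215. They describe the consequence of one occurrence; the documents give no basis for its probability. The efficacy analyses are unaffected.

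**What to change.** Replace the last sentence of SAP 3.1.3 and its counterpart in protocol 11.5 with a rule to this effect:

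- Any subject who receives at least one RSLV-132 infusion is summarized for safety under RSLV-132. In a placebo starter, AEs, ADA results and patient-years count from the first RSLV-132 infusion onward.
- A placebo starter's AEs and exposure before that infusion are flagged and listed separately, and are left out of the RSLV-132 numerator and denominator.
- RSLV-132 starters who receive placebo stay under RSLV-132, as now.

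This removes the need to define the original group and settles the single wrong infusion. SAP 10.1, 10.1.2 and 10.3 should refer to the rule so that numerators and patient-years follow it.

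The cost is one replaced rule in each document and slightly more programming. If the case occurs, some placebo person-time is lost: 7, 84 or 154 days for a switch at Day 8, 85 or 155, so at most 154/365.25 = 0.42 patient-years for one subject. The change should be made before the blind is broken.
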